#### Red Blood Cell Transfusions

Investigators should use their local institution's transfusion guidelines when determining whether to transfuse a study subject.

Subjects who initiate either rescue therapy, ESA Rescue Therapy or Red Blood Cell Transfusion, will be required to stop study drug treatment and will be discontinued from the study. See [Section 7.6.3](#) for subjects who discontinue study drug or withdraw early from the study.

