4.2 General Presentation Considerations

Pre-treatment Hb is defined as the average of 3 Hb values obtained prior to treatment based on most recently 2 qualifying screening Hb values and the Hb value at the baseline visit (Day 1). 'Pre-treatment' for other variables is defined as the last available pre-treatment assessment. In general, this is the value at the Baseline Visit. 'End of Treatment (EOT)' is defined as the assessment on the EOT form labeled as 'Week 16 Visit', even if other values closer to Day 113 are available. For the analysis purpose, only actual visit will be used and hence EOT will be presented as "Week 16". In the summary table, EOT of early withdrawal will not be counted but only be displayed in the listing for reference purpose. 'Treatment Day' will be calculated relative to start of dosing at Baseline Visit (i.e. Treatment Day = Assessment Date - Baseline Visit Date + 1).

Continuous data will be summarized in terms of the mean, standard deviation (SD), median, minimum, maximum and number of observations, unless otherwise stated. The minimum and maximum will be reported to the same number of decimal places as the raw data recorded in the database. The mean and median will be reported to one more decimal place than the raw data recorded in the database. The SD will be reported to two more decimal places than the raw data recorded in the database. In general, the maximum number of decimal places reported shall be four for any summary statistic.

Categorical data will be summarized in terms of the number of subjects providing data at the relevant time point (n), frequency counts and percentages. Any planned collapsing of categories will be detailed in the SAP text and the data displays.

Percentages will be presented to one decimal place. Percentages will not be presented for zero counts. Percentages will be calculated using n as the denominator. If sample sizes are small, the data displays will show the percentages, but any textual report will describe frequencies only.

Changes from baseline in categorical data will be summarized using shift tables where appropriate.

P-values greater than or equal to 0.001, in general, will be presented to three decimal places. P-values less than 0.001 will be presented as “<0.001”.

Confidence intervals will be presented to one more decimal place than the raw data.

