The number and percentage of subjects above / within / below target range who are maintained within the target range at their previous visit after Week 6 will be provided by treatment group.

The effect of treatment in terms of the proportion of subjects within target Hb level at Week 6 will be analyzed using Fisher's exact test. Three post-hoc pairwise comparison, i.e., placebo vs 150 mg, placebo vs 300 mg, and placebo vs 600 mg, will be done.

A by-subject listing will be provided.

Increase in Hb from pre-treatment average

A summary of the cumulative number and percentage of subjects who achieved a ≥ 1 g/dL increase in Hb from pre-treatment average will be provided by treatment group. In addition, the cumulative proportion of subjects within target range will be displayed graphically from baseline visit to follow up visit by treatment group.

The effect of treatment in terms of the proportion of subjects who achieved a ≥ 1 g/dL increase in Hb from pre-treatment average will be analyzed using Fisher's exact test. Three post-hoc pairwise comparison, i.e., Placebo vs 150 mg, placebo vs 300 mg, and placebo vs 600 mg, will be done.

Hematocrit, RBC count, and reticulocyte count (CBC)

Hematocrit, RBC count, and reticulocyte count (both absolute and percent) will be analyzed as secondary efficacy variables.

The following summaries will be provided:

- A summary of hematocrit, RBC count, and reticulocyte count (both absolute and percent) by treatment group and time point. 1st and 3rd quartiles (Q1, Q3) as well as the mean, SD, median, minimum, maximum and number of observations will be presented.
- A summary of the change (absolute and percent) from baseline in hematocrit, RBC count, and reticulocyte count (both absolute and percent) by treatment group and time point.
- Box plots of absolute changes from baseline in hematocrit, RBC count, and reticulocyte count for each treatment group at each post-treatment time point.

The effect of treatment in terms of the change from baseline to Week 6 in hematocrit and RBC count and reticulocyte count (both absolute and percent) will be analyzed using ANCOVA. The statistical model will assess the main effect of treatment, adjusted for baseline measurement. LS-means for each treatment and their 95% CIs will be presented. Three post-hoc pairwise comparison, i.e., Placebo vs 150 mg, placebo vs 300 mg, and placebo vs 600 mg, will be done. Unadjusted ANOVA will be performed for sensitivity.

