A by-subject listing of hematocrit, RBC count, and reticulocyte count (both absolute and percent) will be provided by treatment group.

Iron indices and hepcidin

Iron indices (i.e., iron, TIBC, TSAT, and ferritin) and hepcidin will be analyzed as secondary efficacy variables.

The following summaries will be provided:

- A summary of iron indices and hepcidin by treatment group and time point
- A summary of the change (absolute and percent) from baseline in iron indices and hepcidin by treatment group and time point
- Box plots of absolute changes from baseline in iron indices and hepcidin for each treatment group at each post-treatment time point

A by-subject listing of iron indices and hepcidin will be provided by treatment group.

Rescue therapy & ESA administration

Initiation of rescue therapy will be analyzed.

The following Rescue therapy summaries will be provided:

- A summary of the number and percentage of subjects requiring rescue with RBC transfusion from baseline to the end of the primary efficacy period (Week 6) and the end of the dose adjustment and maintenance period (Week 16)
- A summary of the number and percentage of subjects requiring rescue with ESAs from baseline to the end of the primary efficacy period (Week 6) and the end of the dose adjustment and maintenance period (Week 16) An ESA rescue is defined to fulfill the following 4 criteria simultaneously:
 1. ESA administration, and
 2. ESA administered because the subject experienced a clinically significant worsening of their anemia or symptoms of anemia, and
 3. ESA administered because the subject's Hb level is <9.0 g/dL, and
 4. Subjects' reason for early study withdrawal is because of "Worsening of anemia requiring ESA rescue or blood transfusion".

The following ESA administration summaries will be provided:

- A summary of the number and percentage of subjects requiring administration with ESAs from baseline to the end of the primary efficacy period (Week 6) and the end of the dose adjustment and maintenance period (Week 16)

The effect of treatment in terms of the proportion of subjects requiring RBC transfusion / ESAs administration will be analyzed using Fisher's exact test. Three post-hoc pairwise comparison, i.e., Placebo vs 150 mg, placebo vs 300 mg, and placebo vs 600 mg, will be done.

By-subject listings of rescue therapies and ESA administration will be provided by treatment group.

Average Daily Dose

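### The per-visit denominator in SAP 4.2 does not fit the cumulative response summaries in SAP 4.7.3: taken literally, the percentage can rise with no new responder and can pass 100%

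*SAP*

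**What the plan says.** SAP 4.2 (General Presentation Considerations) gives the general rule for categorical outputs: "Categorical data will be summarized in terms of the number of subjects providing data at the relevant time point (n), frequency counts and percentages". It then fixes the denominator: "Percentages will be calculated using n as the denominator". No exception is attached to that sentence. The same section keeps the end-of-treatment value of an early withdrawal out of the summary tables, and SAP 4.7.1.3 analyses secondary endpoints on observed data without imputation. A subject who has left is therefore not in n at later visits.

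SAP 4.7.3, under the increase in Hb from the pre-treatment average, asks for two outputs that accumulate over time:

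- "A summary of the cumulative number and percentage of subjects who achieved a ≥ 1 g/dL increase in Hb from pre-treatment average", by treatment group;
- a plot in which "the cumulative proportion of subjects within target range will be displayed graphically from baseline visit to follow up visit by treatment group".

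Neither has a denominator of its own. The Fisher exact test on the responder proportion, in the same subsection, states neither a time point nor a denominator. SAP 4.7.3 names MITT and PP as the populations for these endpoints, but a population is not a denominator when 4.2 defines n separately.

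**The concern.** A count of subjects in a category at one visit and the number with data at that visit belong together: someone who has left is in neither. A cumulative count is different, because it holds everyone who has had the event so far, including those who have since gone. Set over n at the visit, it mixes two sets of subjects. The percentage can then climb because people leave and not because anyone responds, and nothing stops it at 100%. A subject who misses one visit and returns would make a cumulative percentage go up and then down.

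SAP Amendment 1 (Change#9) made the responder summary cumulative and added the plot. The change list shows no matching entry for 4.2.

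What is at stake is the reading of supportive dose-response displays in a trial meant to inform a Phase 3 starting dose, with about 12 subjects per group, where one subject is 8.3 percentage points. If the same counts feed the Fisher test, its table may not be valid.

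**Working it through.** The documents state no responder percentage, so there is no planned figure to reproduce.

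**Inputs**

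- N = 12 per group (SAP 4.10; Protocol 11.2).
- Dropout of 10% overall, with no rate by group (Protocol 11.2). One of 12 is 8.3%, so one leaver per group is close to this.
- r, cumulative responders, and k, leavers, per group: **assumptions**, varied below. n = 12 − k.

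**Step 1. Literal rule against a fixed denominator.** The literal figure is r/n and the fixed figure is r/N. Their ratio is N/n and their difference is r(1/n − 1/N).

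The ratio is 12/11 = 1.09, 12/10 = 1.20 and 12/9 = 1.33 for 1, 2 and 3 leavers.

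| r | k | n | r/n | r/12 | Difference (points) |
|---|---|---|---|---|---|
| 6 | 1 | 11 | 54.5% | 50.0% | 4.5 |
| 6 | 2 | 10 | 60.0% | 50.0% | 10.0 |
| 6 | 3 | 9 | 66.7% | 50.0% | 16.7 |
| 1 | 3 | 9 | 11.1% | 8.3% | 2.8 |
| 1 | 4 | 8 | 12.5% | 8.3% | 4.2 |
| 9 | 1 | 11 | 81.8% | 75.0% | 6.8 |
| 11 | 2 | 10 | 110.0% | 91.7% | 18.3 |

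With r = 6 the figure goes from 50.0% to 66.7% with no new response. With r = 11 and n = 10, the non-responder cell of a Fisher table would be 10 − 11 = −1. With r = 0 there is no effect at any dropout.

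**Step 2. Against the true rate.** r/N is a reference, not the truth. Let p be the true cumulative response rate, holding among those who stay; d the dropout; and q the share of leavers who had responded before leaving. Then

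- r/n tends to [(1 − d)p + dq]/(1 − d) = p + qd/(1 − d);
- r/N tends to (1 − d)p + dq.

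With p = 0.5 and d = 0.10:

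- q = 0: r/n = 50.0%, r/N = 45.0%;
- q = 0.25: r/n = 50.0 + 2.8 = 52.8%, r/N = 47.5%;
- q = 0.5: r/n = 50.0 + 5.6 = 55.6%, r/N = 50.0%.

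The literal rule overstates the rate only if some leavers had already responded. The fixed denominator errs low when fewer leavers had responded than p.

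**Step 3. Direction for the dose comparison.** Two assumed cases:

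- Placebo r = 1, k = 3; high dose r = 10, k = 1. Fixed: 83.3 − 8.3 = 75.0 points. Literal: 90.9 − 11.1 = 79.8. The gap widens.
- Placebo r = 6, k = 3; high dose r = 9, k = 1. Fixed: 75.0 − 50.0 = 25.0 points. Literal: 81.8 − 66.7 = 15.2 from unrounded values. The gap narrows.

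The sign depends on counts that the documents do not give.

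**The case against.** The strongest reply is that the inflation is inferred. The SAP does not say whether the time point of a cumulative table is the visit itself or the whole period up to it. On the second reading n is essentially the MITT group, since MITT membership requires a post-baseline Hb value, and the problem disappears. A programmer who saw 110% would presumably stop. This stands as far as it goes: the error is a consequence of the literal rule, not a certainty. But the rule is written without exception, and two programmers could properly produce different tables. Restricting both counts to subjects still present avoids impossible figures, but it discards responders who left, so the output is no longer cumulative.

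Materiality is also limited. SAP 4.7.1.4 calls the secondary variables supportive with no labeling claim intended, tables show counts beside percentages, and SAP 4.2 has small samples described in text by frequencies only. The displays and the plot would still carry the percentages.

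Three stronger readings are tempting and are not supported:

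- **That every percentage in the SAP is affected.** The disposition, deviation and population tables (SAP 4.3.1, 4.3.2, 4.4) use all randomized subjects, and single-visit percentages are internally consistent.
- **That rescue rates are overstated in the same way.** Protocol 8.2.6 says rescued subjects "will be required to stop study drug treatment and will be discontinued from the study", so a reader might infer that 2 of 12 rescued (16.7%) becomes 2/10 (20%). But SAP 4.7.3 defines a window: "A summary of the number and percentage of subjects requiring rescue with ESAs from baseline to the end of" each period. Rescue is reviewed at every post-baseline visit (Protocol 9.3.1), including the end-of-treatment and follow-up visits asked of early leavers (7.6.3, 9.4.8, 9.4.9). Rescued subjects do provide data for that window. The SAP's definition of ESA rescue also requires withdrawal for worsening anemia, so a denominator of those still present would exclude every case.
- **That the groups with most dropout are worst affected, so the dose difference shrinks.** The ratio N/n is largest there, but the gain in points need not be: 4.2 with one responder and four leavers, against 6.8 with nine responders and one leaver. Subjects leaving for worsening anemia are likely to be non-responders, which puts q near 0 and the bias near nil.

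**Conclusion.** The point holds as a mismatch between a general rule and two specific outputs. Read literally at each visit, SAP 4.2 makes the cumulative response percentage and the cumulative target-range proportion exceed r/N by the factor N/n, and allows values above 100%. At about the planned dropout the factor is 1.09. Against the true rate, the overstatement at 10% dropout with half responding is 0 to 5.6 points as q runs from 0 to 0.5. These sizes rest on assumed responder and leaver counts and on n being taken visit by visit.

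No direction for the comparison between doses can be claimed. The primary ANCOVA, with LOCF in MITT, is unaffected. The PP population requires efficacy data through Week 6, so there the issue could arise only after that visit. It is worth correcting because the repair is cheap and the Fisher test on response is otherwise not fully specified.

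**What to change.** Add to SAP 4.7.3, in words to this effect:

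> For the cumulative percentage with an Hb rise of at least 1 g/dL, the cumulative target-range proportion, and the Fisher exact test on the 1 g/dL response, the denominator at every visit is the number of subjects in the treatment group of the population being analysed: MITT N for MITT outputs, PP N for PP outputs. A subject who leaves without the event counts as not having had it. This is an exception to the observed-data rule in 4.7.1.3.

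State the time point of that Fisher test as well; Week 6 is the last visit before the placebo group is switched to vadadustat. Keep n at the visit for single-visit summaries. The same fixed denominator may be written in for the rescue and ESA-administration windows, for clarity only.

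The cost is wording. The downside is that leavers without the event become non-events, which is slightly conservative for response: 45.0% against a true 50.0% in the case above where no leaver had responded. A Kaplan-Meier cumulative incidence could be shown alongside if that matters.

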4.3 Study Subjects

4.3.1 Disposition of Subjects

A clear accounting of the disposition of all subjects who enter the study will be provided, from screening to study completion.

The summary of the following subject disposition will be presented.

- A summary of the number of subjects randomized, the number and percentage of subjects treated (with at least one dose of study medication) and the number and percentage of subjects completed through Week 6 Visit and discontinued by Week 6 Visit by treatment group and overall (Analysis population: All Subjects Randomized). For final analysis, a summary of the number and percentage of subjects completed Week 18 Visit and discontinued from the study by treatment group and overall will be provided (Analysis population: All Subjects Randomized). Withdrawals from the study will also be summarized by major reason.

By-subject listings of eligibility details, randomization details, visit dates and withdrawal/study completion details (including reason for discontinuation and duration of treatment prior to discontinuation) will be provided.

4.3.2 Protocol Deviations

Major protocol deviations are defined as those deviations from the protocol likely to have an impact on the perceived efficacy and/or safety of study treatments. The impact of major protocol deviations on the efficacy and/or safety results will be evaluated prior to unblinding to determine which data and/or subjects, if any, to exclude from the analysis populations (see [Section 4.4](#)),

Protocol deviations and any action to be taken regarding the exclusion of subjects or affected data from specific analyses will be determined in the Protocol Deviation Specification document 20170207 version 2.0.

Protocol deviations will be summarized as following:

A summary of the number and percentage of subjects with a protocol deviation by treatment group and overall and by type of deviation and by period including primary period and dose adjustment and maintenance period. Randomized subjects will be analyzed. A by-subject listing of protocol deviations will be provided.

4.4 Analysis Populations

Upon database release, protocol deviation and analysis population outputs will be produced and will be sent to Sponsor for review. An analysis population classification meeting will be arranged to discuss the outputs and to decide which subjects and/or subject data will be excluded from certain analyses. Decisions made regarding the exclusion of subjects and/or subject data from analyses will be made prior to unblinding and will be documented and approved by Sponsor.

The following summary of analysis population will be provided:

- A summary of the number and percentage of subjects allocated to each analysis population by treatment group and overall (Analysis population: All Subjects Randomized)

A by-subject listing of analysis population details will be provided. This listing will be presented by treatment group and include: site, subject identifier, inclusion/exclusion flag for each population and reason for exclusion from each population. All subjects randomized will appear on this listing.

4.4.1 Analysis Population for the Safety Analyses

The safety summaries and analyses will be based on the **safety population**. The safety population is defined as all enrolled subjects who receive at least 1 dose of study medication. In the event that a subject is allocated the incorrect study treatment as per the study randomization list, subjects will be summarized and analyzed ‘as treated’ i.e. by allocated treatment group.

4.4.2 Analysis Populations for the Efficacy Analyses

The efficacy summaries and analyses will be based on the **modified intent-to-treat (MITT) population**. The MITT population is defined as all randomized subjects who have received at least 1 dose of study medication and have a pre-treatment Hb average defined as the average of the most recently 2 qualifying screening value and the baseline value, and at least one post-baseline Hb measurement. **The post-baseline Hb measurement will exclude the withdrawal Hb and follow-up Hb measurements for discontinued patients.** In the event that a subject is allocated the incorrect study treatment as per the study randomization list, subjects will be summarized and analyzed ‘as randomized’ i.e. by randomized treatment group.

For the efficacy variables, sensitivity analyses will be performed on the **per-protocol (PP) population** to assess the robustness of the study conclusions to the choice of analysis population. The PP population is defined as the subjects in the MITT population who have completed the study and have efficacy data through Week 6, have a study medication compliance of $\geq 80\%$, and do not have any major protocol deviations expected to significantly affect the primary efficacy endpoint. Subjects with major protocol deviations expected to significantly affect the primary efficacy endpoint will be identified and documented prior to data unblinding.

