### 7.6.3 Individual Subject Discontinuation

Subjects permanently discontinuing study drug or withdrawing early from the study prior to the Week 16 visit should complete the Week 16 (EOT) clinical and laboratory assessments within 1 day of stopping study medication, if possible. Such subjects should also complete the 2-week follow-up period and complete the Week 18 visit assessments (see Appendices

[Appendix A](#) and [Appendix B](#)).

For subjects who discontinue study medication, the investigator should resume standard of care treatment, as deemed appropriate.

If a subject does not return for a scheduled visit, every effort should be made to contact the subject.

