#### **11.4.2 Analysis Populations for the Efficacy Analyses**

The modified intent-to-treat (MITT) population is defined as all randomized subjects who receive at least 1 dose of study medication, have a pre-treatment Hb average, and at least one post-baseline Hb measurement. A pre-treatment average value for Hb is defined as the average of 3 values obtained prior to dosing, ie, the 2 qualifying screening values and the baseline value. The MITT population will be based on the treatment to which patients are randomized.

The per-protocol (PP) population will consist of the subjects in the MITT population who have completed the study and have efficacy data through Week 6, have a study medication compliance of  $\geq 80\%$ , and do not have any major protocol deviations expected to significantly affect the primary efficacy endpoint. Subjects with major protocol deviations expected to significantly affect the primary efficacy endpoint will be identified and documented prior to data unblinding.

As sensitivity analyses, efficacy endpoints will also be analyzed using the PP population.

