4.7.1.3 Handling of Missing Data

For the MITT population analyses for the primary efficacy variable, the Last Observation Carried Forward (LOCF) approach will be used to impute missing data for primary efficacy analysis.

Subjects who underwent dose reduction before week 6 will not be analyzed differently from subjects who did not undergo dose reduction. This means we will use the actual Hb at week 6 for all subjects except the missing data, which will be carried from the last Hb before week 6 and after baseline.

- If a Baseline value is missing, the last value prior to baseline will be carried forward to the Baseline value but not to further values during the treatment period.
- For post-Baseline assessments, hemoglobin measurements at end of treatment and follow-up visits are not carried forward. Other than that, the most recent post-baseline assessments to the primary evaluation period (week 6) will be carried forward. Baseline and pre-Baseline values will not be carried forward to the post-Baseline visits.

For the secondary endpoint analyses, data will be used as observed and no imputation method will be used.

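### The SAP stops counting the withdrawal Hb, which narrows the protocol's MITT population without declaring it and leaves a usable pre-rescue value out of the primary analysis; the expected effect is small

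*SAP*

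**What the plan says.** Protocol 11.4.2 places in MITT all randomised subjects who take at least one dose, and who "have a pre-treatment Hb average, and at least one post-baseline Hb measurement". It sets no limit on which post-baseline Hb qualifies.

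SAP 4.4.2 repeats that definition and then adds: "The post-baseline Hb measurement will exclude the withdrawal Hb and follow-up Hb measurements for discontinued patients". SAP section 6.1.3, Change#3, prints the text with and without this sentence. The list of main changes in SAP 6.1.1 does not mention it, and SAP 4.11, on changes to the planned analysis, reads as not applicable.

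Three further rules decide what happens to the value:

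- SAP 4.7.1.3 on imputation: "For post-Baseline assessments, hemoglobin measurements at end of treatment and follow-up visits are not carried forward". It also states: "Baseline and pre-Baseline values will not be carried forward to the post-Baseline visits".
- SAP 4.2 on early withdrawals: "In the summary table, EOT of early withdrawal will not be counted but only be displayed in the listing for reference purpose".
- Protocol 7.6.3 on collection: subjects who stop early "should complete the Week 16 (EOT) clinical and laboratory assessments within 1 day of stopping study medication, if possible". Protocol 9.4.8 and 9.5.9 include a CBC, and so an Hb, at that visit.

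Protocol 8.2.6 requires anyone who starts ESA rescue or receives a transfusion to stop study drug and leave the study.

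**The concern.** The protocol defines its own primary efficacy population, and the SAP makes it smaller. The value set aside is one the protocol asks sites to collect, close to the last dose where possible. The SAP gives no reason for setting it aside.

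The loss is not entirely random. A subject rescued before Week 6 must discontinue and so falls under these rules. Depending on timing, that subject either disappears from the primary analysis or contributes an Hb from before the end of treatment. With 12 subjects per arm, each one lost is 8% of an arm (1/12). The objective is a dose-response that sets the Phase 3 starting dose, so a distortion in one arm matters even if the 600 mg comparison is safe.

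**Working it through.** **The plan's own figure.** Protocol 11.2 assumes a difference of 1.35 g/dL, SD 0.9 g/dL, 12 per group, 10% dropout and two-sided alpha 0.05, and claims power above 85%. After dropout 12 × 0.9 = 10.8, or 10 whole subjects per group. With 10 per group the noncentrality is 1.35 / (0.9 × √(2/10)) = 3.35, and a two-sample t-test has power 88.7% (91.2% with 10.8). The claim is reproduced and is not in dispute. With 12 per group power is 93.9%, with 11 it is 91.7%.

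**Who is affected.** The first post-baseline Hb is scheduled at Week 2 (Day 15) and the next at Week 4 and Week 6.

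| Subject stops before Week 6, with | Protocol 11.4.2 | SAP 4.4.2 and 4.7.1.3 |
|---|---|---|
| withdrawal Hb only | in MITT | out of MITT, no value to analyse |
| Week 2 or Week 4 Hb, then withdrawal Hb | in MITT, imputation not specified | in MITT, Week 2 or Week 4 Hb carried forward |
| follow-up Hb only | in MITT as worded | out of MITT, no value to analyse |

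**How many.** At 10% dropout: 12 × 0.10 = 1.2 per arm and 48 × 0.10 = 4.8 overall. This is a ceiling if the 10% refers to the first six weeks (assumed).

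**Size when an earlier value is carried.** If k of 12 subjects have a withdrawal Hb that is g below the carried value, the arm mean is raised by k × g / 12. The documents give no g, so the range is assumed.

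| | g = 0.5 | g = 1.0 | g = 1.5 |
|---|---|---|---|
| k = 1 | 0.04 | 0.08 | 0.13 |
| k = 2 | 0.08 | 0.17 | 0.25 |

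For gradual decline, assume 0.1 to 0.2 g/dL per week and an average of one week since the last visit (half the two-week interval). At 10% dropout the shift is 0.10 × 0.1 = 0.01 to 0.10 × 0.2 = 0.02 g/dL. A rough placebo simulation (assumed baseline 9.2, SD 0.6, the same slopes, rescue below 8.0 or 8.4) gave 0.006 to 0.023 g/dL, with 1.5% to 6.6% of placebo subjects lost from MITT. It is an order of magnitude only. Its triggers are not the protocol's confirmed Hb below 9.0 g/dL, and its rescue share of 10% to 39% reaches well above the planned dropout.

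**Size when the subject is dropped.** If the full placebo mean is 0 and k subjects with change v are removed, the mean becomes −k × v / (12 − k). For v from −0.5 to −1.5 g/dL this is +0.05 to +0.14 for one subject and +0.10 to +0.30 for two.

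**Scale.** One arm's standard error is 0.9 / √12 = 0.26 g/dL, so a shift of 0.083 is about a third of it. If that shift falls on placebo, the expected difference is 1.35 − 0.083 = 1.267 and power at 12 per group goes from 93.9% to 90.9%.

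**Whether another planned analysis recovers the value.** The per-protocol set is a subset of MITT that needs efficacy data through Week 6. The unadjusted ANOVA (SAP 4.7.1.2) only removes the covariate. Neither brings the withdrawal Hb back.

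**The case against.** The case for leaving the SAP alone has real substance.

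- **Imputation.** A reader might infer that both SAP rules contradict the protocol. Only the MITT sentence does. The protocol has no LOCF rule, and its section 11 leaves the details of the primary analysis to the SAP. This stands.
- **On-treatment status.** It is tempting to treat every withdrawal Hb as an on-treatment value. Protocol 7.6.3 qualifies the one-day target as applying where possible, and nothing requires the sample to precede rescue. A post-transfusion Hb would be raised, and excluding it is sound. The SAP, however, excludes all withdrawal values without that distinction.
- **Hidden falls.** A reader might infer that the rule conceals the worst Hb values. ESA rescue normally needs two consecutive Hb below 9.0 g/dL (Protocol 8.2.6), so the carried value may already show the fall. The gap arises mainly where confirmation is waived or a transfusion is given abruptly. The SAP does not say clearly whether an unscheduled confirmatory Hb may be carried.
- **Breadth.** The rule applies to every discontinuer. Protocol 7.6.2 also lists toxicity, withdrawn consent, pregnancy, transplant and other reasons, so only part of the exclusion depends on outcome.
- **Traceability.** Change#3 prints both texts, exclusions are settled before unblinding, and the values appear in listings. This softens the silence in SAP 4.11 but does not replace a declaration or an analysis.

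**Conclusion.** The point holds in a limited form. SAP 4.4.2 narrows a population that the protocol itself defines, SAP 4.11 does not say so, and the two SAP rules together keep a timely pre-rescue Hb out of the primary analysis.

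The expected effect is small against 1.35 g/dL: at most about one subject per arm at 10% dropout, 0.01 to 0.02 g/dL under gradual decline, and 0.08 g/dL for one abrupt 1.0 g/dL fall in 12. All of these rest on assumed declines and gaps, since the documents give no rescue rate or withdrawal values.

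A reader might infer that the rule favours the drug. The documents do not support that. If it falls on placebo, the treatment difference shrinks. If it falls on a vadadustat arm, that arm looks better than it was. The second case is the more relevant one for the lower doses reached by the step-down tests and for the choice of starting dose.

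**What to change.** In SAP 4.4.2 and 4.7.1.3 together, count a withdrawal Hb for both MITT membership and LOCF when all three conditions hold:

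1. it is drawn by the end of the Week 6 window (Day 43 ± 3, so by Day 46);
2. it is drawn within a pre-stated number of days of the last dose. The protocol's own one-day target is the strict option, and the three-day visit window is a looser one;
3. it is drawn before any rescue ESA or transfusion.

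Continue to exclude follow-up and post-rescue Hb. Both sections must change: restoring the protocol's wording alone would admit subjects whose only Hb is a follow-up or post-rescue value, with nothing to analyse. Declare in SAP 4.11 any difference from Protocol 11.4.2 that remains.

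If the present rule is kept, declare and justify it in SAP 4.11 and add a sensitivity analysis of the primary endpoint that includes pre-rescue withdrawal Hb.

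Either way, settle it before the unblinding for the 6-week preliminary analysis. The cost is SAP wording, a date check and the mapping of a few withdrawal values to a visit. No new data are needed.
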